2.3 PARTICIPANT REGISTRATION AND STATUS UPDATE PROCEDURES

2.3.1 Subjects that require pre-screening for MSLN

Participants that do not have pancreatic adenocarcinoma, extrahepatic cholangiocarcinoma or epithelioid mesothelioma must undergo pre-screening for MSLN expression.

Registration and status updates (e.g. when a participant is taken off protocol therapy and when a participant is taken off-study) will take place per CCR SOP ADCR-2, CCR Participant Registration & Status Updates found here.

2.4 TREATMENT ASSIGNMENT PROCEDURES

Cohorts

Number	Name	Description
1	Dose Escalation	1-6 patients per level x2 dose levels
2	Dose Expansion	Up to 15 additional eligible and evaluable patients will be treated to assess the safety of optimal dose for patients with pancreatic cancer or extrahepatic cholangiocarcinoma

Arms

Number	Name	Description
1	Dose Escalation	LMB-100 (escalating doses) + tofacitinib for 3 cycles
2	Dose Expansion	LMB-100 + tofacitinib (at dose determined in dose escalation portion of the study) for 3 cycles. At least 8 subjects must have PDAC.

Arm Assignment

Patients in Cohort 1 will be directly assigned to Arm 1. Patients in Cohort 2 will be directly assigned to Arm 2.

3 STUDY IMPLEMENTATION

3.1 STUDY DESIGN

Schema

- This is a Phase I study which will accrue up to 45 participants.
- Participants will be admitted to the NIH Clinical Center for LMB-100 administration.
- For the dose escalation phase, a 3+3 dose escalation will be used. Two dose levels are planned. A minus dose level could be utilized if de-escalation is necessary.
- Following identification of an optimal dose and schedule, an expansion phase of 15 participants will be initiated at the optimal dose for patients with pancreatic adenocarcinoma and extrahepatic cholangiocarcinoma. At least 8 participants in the expansion phase must have pancreatic adenocarcinoma.
- Participants on the Dose Escalation and Dose Expansion Arms will be treated for a maximum of 3 cycles with the exception described in the next bullet
- Participants on the Dose Escalation and Dose Expansion Arms who appear to be deriving clinical benefit may continue to receive treatment beyond 3 cycles as indicated in Section Error! Reference source not found..

• Toxicities and adverse events will be monitored continuously during treatment and for 30 days beyond the last treatment.

3.1.1 Dose Limiting Toxicity

For the study, a DLT will be defined as any of the following events occurring during the first cycle of treatment (21 days), the DLT evaluation period. Toxicities determined to be unequivocally related to disease progression or intercurrent illness will not be regarded as DLTs. The following will be considered DLTs:

- Any death not clearly due to the underlying disease or extraneous causes
- Transaminitis that meets criteria for Hy's Law: grade ≥2 elevation of AST or ALT with simultaneous elevation of total bilirubin to ≥ 2x ULN while alkaline phosphatase remains < 2x ULN.

Hematological toxicities:

- Grade 4 neutropenia (i.e. absolute neutrophil count (ANC) <0.5 x 10^3 cells/µL for a minimum duration of 7 days)
- Grade 3 and 4 febrile neutropenia (i.e. ANC < 1.0×10^3 cells/µL with a single temperature of >38.3°C or a sustained temperature of ≥38°C for more than one hour; or life-threatening consequences with urgent intervention indicated)
- Grade 4 thrombocytopenia ($\leq 25.0 \times 10^3 \text{ cells/}\mu\text{L}$)
- Grade 3 thrombocytopenia associated with bleeding episodes
- Grade 4 anemia

$\underline{\text{Grade} \geq 3 \text{ non-hematological toxicity with the exception of:}}$

- Grade 3 nausea and vomiting lasting <48 hours occurring in the absence of appropriate anti-emetic treatment
- Grade 3 diarrhea lasting for ≤ 2 days with no fever or dehydration
- Infusion-related reactions up to and including Grade 3. IRRs are not considered to be DLTs since, based on experience with monoclonal antibodies, they are idiosyncratic and not dose-related events. Precautions will be taken if IRRs Grade ≥2 occur (see Section 3.3).
- Asymptomatic grade 3 elevation of ALT, AST, GGT, bilirubin or alkaline phosphatase attributable to study drug that persists for less than 7 days if not violating Hy's Law. (Please note that all grade 4 elevations in these parameters should be considered a DLT)
- Asymptomatic laboratory values (other than ALT, AST, GGT, bilirubin, alkaline phosphatase or creatinine) of Grade 3 that are judged not clinically significant by the investigator.
- Isolated Grade 3 fever (without signs and/or symptoms of an infection) occurring within 48 hours after LMB-100 infusion and resolving within 48 hours to \leq Grade 2 and fully resolved within 1 week.

Other toxicities:

- Any other drug related toxicity considered significant enough to be qualified as a DLT in the opinion of the principal investigator.
- Inability to start cycle 2 within 2 weeks after completing cycle 1 due to drug-related adverse events.

If a participant experiences a DLT of any grade, the investigator will have the option to either stop treatment or to resume the treatment at the next lowest dose level based on best clinical judgment. Patients will be assessed based on the original cohort. This can be done to allow participants who could potentially benefit from LMB-100 to remain on the study drug treatment, if considered the most beneficial therapeutic option for the participant while managing and monitoring the participant's safety risks.

3.1.2 Dose Schedule

The dose schedule is outlined below in **Table 8**. Patients will be enrolled as per standard 3+3 design, if 0 of 3 or <2 of 6 patients experience DLT then dose escalation may proceed. If 2 or more patients experience DLT at any dose level, then dose de-escalation is required.

The rule by which clinical team will decide when to escalate or de-escalate have been explained in **Table 9**.

Dose LevelLMB-100 infusion (mcg/kg)Given days 4, 6, 8Level -165Level 1100Level 2140

Table 8

Note: A weight-based dose cap will be applied. LMB-100 dose for patients weighing more than 100 kg will be calculated as if they weigh 100kg.

*All patients will receive tofacitinib 10 mg BID on days 1-10 of each cycle

Dose escalation will follow the rules outlined in Table 9.

Table 9

Number of Patients with DLT at a Given Dose Level	Escalation Decision Rule
0 out of 3	Enter up to 3 patients at the next dose level
≥ 2	Dose escalation will be stopped. This dose level will be declared the maximally administered dose (highest dose administered). Up to five additional patients will be entered at the next lowest dose level to complete a max cohort of 6.
1 out of 3	 Per PI discretion, follow instructions for ≥ 2 DLT OR Enter up to 3 more patients at this dose level. If 0 of these 3 patients experience DLT, proceed to the next dose level. If 1 or more of this group suffer DLT, then dose escalation is stopped, and this dose is declared the maximally administered dose. UP to five additional patients will be entered at the next lowest dose level to complete a max cohort of 6.
≤1 out of 6 at highest dose level below the maximally administered dose	This is the MTD and is generally the recommended phase 2 dose. At least 6 patients must be entered at the recommended phase 2 dose.

3.1.3 Treatment Extension

Participants who complete 3 cycles of therapy with LMB-100/tofacitinib and appear to be deriving clinical benefit as evidenced by lack of progression on CT scan and decreasing serum tumor marker (in patients with serum tumor marker that has historically followed their disease trend) may continue to receive additional cycles of treatment at the discretion of the PI until unacceptable toxicity or patient is no longer thought to be benefiting, or PI's decision to discontinue treatment. If a participant is offered treatment extension but refuses, he/she will be removed from protocol therapy. Participants offered treatment extension may defer immediate treatment with study drugs to take a treatment holiday or to receive other intervening treatments (including investigational treatments). If a participant chooses to defer treatment extension beyond 6 weeks or to have a different intervening therapy, the PI may require to repeat some screening safety evaluations before reinitiating LMB-100/tofacitinib and will require washout periods and criteria consistent with those described in Sections 2.1.1.8, 2.1.1.9 and 2.1.1.10. Safety monitoring while receiving treatment extension will continue as described in the Study Calendar. Limited research labs will be taken as described in Sample Collection Schedule (Section 5.2).

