1.1.3 Exploratory Objectives

- To obtain preliminary assessment of activity including change in appropriate serum tumor markers with treatment, objective response rate (ORR), disease control rate after 3 cycles (~9 weeks) of treatment (DCR), progression free survival (PFS) and overall survival (OS)
- Evaluate association between anti-LMB-100 antibody titer and peak serum drug level
- To examine the relationship between MSLN expression and response to treatment
- To evaluate changes in the tumor microenvironment following treatment with LMB-100 plus tofacitinib
- To assess changes in circulating immune cell and cytokine levels caused by the treatment
- For treatment extension: To determine whether to facitinib can continue to prevent ADA formation beyond 3 cycles of treatment regardless of whether patients had another intervening therapy or not.

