3.4 STUDY CALENDAR

Unless otherwise specified, screening assessments must occur within 28 days prior to registration for study treatment. Cycle 1, day 1 assessments may occur up to 7 days prior to treatment initiation. If screening tests were performed within this window, then they do not need to be repeated on C1D1. Dosing cycles may be delayed for up to one week or started up to 2 days early to accommodate schedule conflicts, federal holidays and inclement weather, etc. They may be delayed for up to two weeks due to toxicity. There is no time limit on dosing cycle delays for patients receiving treatment extension.

			All Cycl	es (21 da	ys)					Post T	herapy
Procedure	Screening	Day 1	Day 3*	Day 4	Day 6	Day 8	Day 9	Day 15	Day 21	Safety Follow Up Visit ⁷	Long Term Follow Up ¹¹
Tofacitinib		ad	ministered	BID days	1-10 of ea	ach cycle					
Prophylactic anti- coagulation		Khorana Score < 2: administer daily on days 1-11 of each cycle Khorana Score ≥ 2: administer throughout treatment until 14 days after last dose of tofacitinib/ LMB-100									
LMB-100				Х	Х	Х					
History and PE	Х	C1 only	Х		Х	Х				Х	
Weight			Х		Х	Х	C1 only			Х	
Height			C1 only								
Vital signs ¹	Х	C1 only	Х	Х	Х	Х	C1 only			Х	
ECOG Performance Status	X	C1 only	X							Х	
Labs ²	X	C1 only	X		Х	Х		C1 only ¹⁴	C1 only ¹⁴	Х	
D-dimer		C1 only	Х			Х					
Cholesterol Panel		C1 only								Х	
TBNK		C1 only	C1 and C3 only				C1 only				
1,25-dihydroxy Vit D	Х									Х	

Abbreviated Title: LMB100 + *tofacitinib in PDA Version Date:* 08/19/20

			All Cycl	es (21 da	ys)					Post T	herapy
Procedure	Screening	Day 1	Day 3*	Day 4	Day 6	Day 8	Day 9	Day 15	Day 21	Safety Follow Up Visit ⁷	Long Term Follow Up ¹¹
Hepatitis and HIV screening panel	Х										
IGRA	Х										
Urinalysis	Х		Х		Х	Х				Х	
Urine albumin and creatinine	C1 only		C1 only		C1 only	C1 only					
Pregnancy test ³	Х		Х								
Confirmation of Dx ⁴	Х										
Assessment of tumor MSLN expression ^{4, 5}	X										
CT CAP and/or MRI ⁸	X	•	cles of stud	•		days				Х	Х
CA 19-9-or appropriate tumor-specific marker ⁵			Х							X	
Doppler U/S of bilateral lower extremities		Optional ¹⁵									
ECG	X		C1 only			C1 only				X	
Echocardiogram	Х										
Ambulatory Oxygen Saturation	Х										
Chest X-ray			X ⁹								
NIH Advance Directives Form ⁶		C1 only ⁶									
Biopsy	X ¹³	C1 only ¹²	C2 only 12								

Abbreviated Title: LMB100 + tofacitinib in PDA *Version Date:* 08/19/20

			All Cycl	es (21 da	ys)					Post T	herapy

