4 CONCOMITANT MEDICATIONS/MEASURES

4.1.1 Permitted Therapy

Concomitant therapy includes any medication (e.g., prescription drugs, over-the-counter (OTC) drugs, approved dietary and herbal supplements, nutritional supplements) used by a participant from the screening period until the follow-up visit. If any treatment is given within 4 weeks prior to screening this should be reported to the investigator and recorded in the eCRF.

All therapy and/or medication administered to manage adverse events should be recorded on the Adverse Event eCRF.

4.1.2 **Prohibited Therapy**

Patients should be treated for all concomitant conditions and adverse events according to accepted standards of medical care at the discretion of the investigator. The following treatments are not permitted during the study:

- Any other investigational therapy
- Cytotoxic chemotherapy agents other than study agents
- Radiotherapy. Note: palliative radiotherapy is allowed.

- Strong inhibitors or inducers of CYP3A4 (as can be found here: **Flockhart Table** or in another frequently updated source)
- Any medications or treatments that may adversely affect the immune system such as allergy injections, immune globulin, interferon, immunomodulators, cytotoxic drugs, or systemic corticosteroids (oral or injectable) at doses higher than needed for adrenal replacement (except as specified as part of protocol treatment).
- Other systemic anti-neoplastic agents and targeted therapies
- Live vaccines

If any anti-neoplastic or investigational therapies listed above are needed, the patient will be considered to have evidence of progressive neoplastic disease and have experienced treatment failure with study treatment and should be withdrawn from study treatment.

All concomitant treatments must be documented in the eCRF.

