6.3.3.3 Evaluation of Best Overall Response

The best overall response is the best response recorded from the start of the treatment until disease progression/recurrence (taking as reference for progressive disease the smallest measurements recorded since the treatment started). The patient's best response assignment will depend on the achievement of both measurement and confirmation criteria.

Target Lesions	Non-Target Lesions	New Lesions	Overall Response	Best Overall Response when Confirmation is Required*
CR	CR	No	CR	≥4 wks. Confirmation**
CR	Non- CR/Non-PD	No	PR	
CR	Not evaluated	No	PR	>4 wks. Confirmation**
PR	Non- CR/Non- PD/not evaluated	No	PR	
SD	Non- CR/Non- PD/not evaluated	No	SD	Documented at least once ≥4 wks. from baseline**
PD	Any	Yes or No	PD	
Any	PD***	Yes or No	PD	no prior SD, PR or CR
Any	Any	Yes	PD	

For Patients with Measurable Disease	(i.e., Target Disease)
--------------------------------------	------------------------

new lesion.

** Only for non-randomized trials with response as primary endpoint.

In exceptional circumstances, unequivocal progression in non-target *** lesions may be accepted as disease progression.

Note: Patients with a global deterioration of health status requiring discontinuation of treatment without objective evidence of disease progression at that time should be reported as "symptomatic deterioration." Every effort should be made to document the objective progression even after discontinuation of treatment.

New Lesions	Overall Response	
No	CR	
No	Non-CR/non-PD*	
No	not evaluated	
Yes or No	PD	
Yes	PD	
	No No No Yes or No	

For Patients with Non-Measurable Disease (i.e., Non-Target Disease)

* 'Non-CR/non-PD' is preferred over 'stable disease' for non-target disease since SD is increasingly used as an endpoint for assessment of efficacy in some trials so to assign this category when no lesions can be measured is not advised

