6.3.5 Progression-Free Survival

PFS is defined as the duration of time from start of treatment to time of progression or death, whichever occurs first.

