10.3 POPULATIONS FOR ANALYSES

10.3.1 Evaluable for toxicity

All patients who receive treatment during dose escalation will be reported. Any patient who receives any study drug treatment and experiences a DLT related to study drug within 21 days of initial treatment is evaluable. Otherwise, patients evaluable for DLT must: 1) receive all doses of study drugs, 2) be followed for study drug toxicity for at least 21 days after the administration of the first dose of LMB-100.

In the expansion phase, up to 15 evaluable patients who can have their drug levels assessed in cycle 2 will be included in analyses. Up to 5 patients will be replaced if they have PD before C2, but if more than 5 patients progress before C2, then no further patients will be accrued as soon as this can be determined.

10.3.2 Evaluable for objective response:

Only those patients who have measurable disease present at baseline, have received at least one cycle of therapy, and have had their disease re-evaluated will be considered evaluable for response. These patients will have their response classified according to the definitions stated below. (Note: Patients who exhibit objective disease progression prior to the end of cycle 1 will also be considered evaluable.) Responses or progressions noted in patients receiving treatment extension will be recorded in the study database but will not be reported in the aggregate objective response rate, which only corresponds to assessments taken prior to the start of a 4th cycle.

10.3.3 Evaluable Non-Target Disease Response:

Patients who have lesions or tumor marker present at baseline that are evaluable but do not meet the definitions of measurable disease, have received at least one cycle of therapy, and have had their disease re-evaluated will be considered evaluable for non-target disease. The response assessment is based on the presence, absence, or unequivocal progression of the lesions or increase in tumor marker.

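### Treatment extension allows other anti-cancer therapy before cycle 4, contradicting sections 4.1.2 and 3.5, and the exploratory response, PFS and ADA analyses do not say how data after that therapy are handled

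*Combined protocol and SAP*

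**What the plan says.** **Permission.** Under section 3.1.3, participants offered extension after cycle 3 "may defer immediate treatment with study drugs to take a treatment holiday or to receive other intervening treatments (including investigational treatments)". On return they must meet the washout periods of 2.1.1.8 (14 days for systemic treatment) and the blood-count and albumin criteria of 2.1.1.9 and 2.1.1.10. Section 3.4 adds: "There is no time limit on dosing cycle delays for patients receiving treatment extension".

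**Prohibition.** Section 4.1.2 bars other investigational therapy, cytotoxic chemotherapy and other systemic anti-cancer agents during the study. "If any anti-neoplastic or investigational therapies listed above are needed, the patient will be considered to have evidence of progressive neoplastic disease"; the patient also counts as a treatment failure and should be withdrawn from study treatment. Section 3.5 lists the need for a drug prohibited in 4.1.2 as a reason to stop protocol therapy. Neither section mentions 3.1.3.

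**Response.** Section 10.3.2: "Responses or progressions noted in patients receiving treatment extension will be recorded in the study database" but are kept out of the aggregate ORR, "which only corresponds to assessments taken prior to the start of a 4th cycle". Section 6.3.3.3: "The best overall response is the best response recorded from the start of the treatment until disease progression/recurrence".

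**PFS.** Section 6.3.5: "PFS is defined as the duration of time from start of treatment to time of progression or death, whichever occurs first". Section 10.4.9 adds Kaplan-Meier estimation with 95% confidence intervals. Neither has a rule for new therapy.

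**ADA beyond cycle 3.** The extension objective in 1.1.3 asks whether tofacitinib goes on preventing ADA formation "regardless of whether patients had another intervening therapy or not". Section 10.4.9 summarises ADA and peak drug levels after cycle 3 descriptively, and allows a descriptive comparison with earlier cycles to judge the effect of the agent.

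**The concern.** Consider a patient without progression after cycle 3 who is offered extension, takes another drug for some months, and then either returns for cycle 4 or does not.

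Under 3.1.3 this patient is handled as planned. Under 4.1.2 and 3.5 the same therapy is prohibited and leads to withdrawal. The site cannot follow both.

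The analysis has a related gap. Tumour shrinkage on the other drug may be counted as activity of LMB-100/tofacitinib. A low ADA titer at cycle 4 may reflect tofacitinib, the other drug or the time off LMB-100, and the plan does not separate these. In a small single-arm study, one patient can visibly change the preliminary activity figures.

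**Working it through.** **1. Order of events.** Three 21-day cycles last 3 × 21 = 63 days, or 9 weeks. Then come the offer of extension, the other therapy (no maximum duration), the washout and cycle 4. The ORR limit is the start of cycle 4, so every scan taken during the other therapy falls before it. Such scans are foreseeable, because the study calendar continues imaging until progression. If cycle 4 never starts, the limit is never reached, and 6.3.3.3 runs on to progression.

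**2. Status of the patient.**

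| Question | 3.1.3 and 3.4 | 4.1.2 and 3.5 |
|---|---|---|
| May the patient take another anti-cancer or investigational therapy? | Yes, if offered extension | No, during the study |
| May study drugs be restarted? | Yes, after washout, with no time limit | No, withdrawn from study treatment |
| Disease status | Not progressed | Deemed progressed if the therapy is needed |

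Section 3.1.3 removes from protocol therapy a patient who refuses extension, but not one who defers it. A deferring patient is therefore still on protocol therapy, where 4.1.2 and 3.5 apply.

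**3. The plan's own design figures (10.2).** For the rule of 11 or more of 15:
- at a true rate of 50%: (1365 + 455 + 105 + 15 + 1) / 2^15 = 1941 / 32768 = 0.0592, stated as 5.9%;
- at a true rate of 80%: exact binomial tail 0.8358, stated as 83.6%.

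Both reproduce. The cycle 2 endpoint precedes any deferral, so neither figure changes.

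**4. ORR (assumed data).** With an assumed 15 evaluable patients, each response first seen on other therapy adds 1/15 = 6.7 points. Exact 95% intervals:
- 0/15 = 0% (0 to 21.8)
- 1/15 = 6.7% (0.2 to 31.9)
- 2/15 = 13.3% (1.7 to 40.5)

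**5. PFS (assumed data).** Take 15 patients: 7 progress at week 6, 3 at week 9, and 5 reach extension. Of these 5, k start other therapy at week 10 and progress at week 27; the rest progress at week 18.

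| | 6.3.5 as written | Censored at new therapy |
|---|---|---|
| PFS at week 17, k = 1, 2, 3 | 33.3% (5/15) throughout | 33.3% throughout |
| PFS at week 20, k = 1, 2, 3 | 6.7%, 13.3%, 20.0% (k/15) | 0% |
| Median | week 9 | week 9 |

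The choice moves the tail by 6.7 points per affected patient and leaves the median alone.

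**6. ADA.** Section 1.2.3.1 reports that pentostatin plus cyclophosphamide delayed antibodies to SS1P, a related immunotoxin, in most patients. Section 1.2.9 says that the lymphocyte depletion often takes months to reverse. Section 4.1.2 counts cytotoxic drugs among treatments that can harm the immune system. Against this, the washout for systemic treatment is 14 days. By the protocol's own account, a low titer after some intervening therapies could come from that therapy. Waning during a long gap is a further possibility, on which the documents give no data.

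**The case against.** Several stronger readings are tempting, and the documents do not support them.

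- **A reader might infer that 10.3.2 plainly credits another drug's responses to the study regimen.** It does not. Its first half keeps results in patients receiving extension out of the aggregate ORR, so the apparent intent is to confine ORR to cycles 1 to 3. What stands is an ambiguity: a patient who has deferred is arguably not yet receiving extension, and the only explicit time limit is cycle 4.
- **A reader might infer that the patient becomes a PFS event under 4.1.2.** Section 6.3 assesses progression by RECIST 1.1, and no endpoint definition imports the deemed progression of 4.1.2, which is a concomitant-medication rule. It is also triggered by need, whereas 3.1.3 covers a choice. The conflict over permission and withdrawal remains.
- **A reader might infer that pooling ADA results is an oversight.** No cut-off governs ADA. Inclusion regardless of intervening therapy is a declared exploratory aim, and 10.4.9 neither prescribes pooling nor forbids a split. The washout reduces carry-over but, given the months-long depletion in 1.2.9, need not remove it.
- **A reader might infer that the PFS definition is wrong.** It is usable. Following patients through new therapy and censoring at it are both defensible, and censoring can be informative.
- **The size is soft.** Section 10.3.2 is not limited to the expansion cohort. With 20 patients (15 plus 5 replacements) one response is 1/20 = 5.0 points; with 27 (12 plus 15) it is 1/27 = 3.7 points. Fewer evaluable patients would make it larger.

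**Conclusion.** The point holds for exploratory endpoints only. Sections 3.1.3 and 3.4 contradict 4.1.2 and 3.5 on whether a patient may take other therapy and return, and must be reconciled. Section 10.3.2 does not clearly exclude a response first seen on intervening therapy. Section 10.4.9 relates ADA levels after cycle 3 to the agent with no stated split by what was given in between. PFS lacks a stated rule for new therapy.

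One misattributed response is worth 6.7 points of ORR on an assumed denominator of 15. The PFS effect is confined to the tail in the assumed example. How many patients will defer, or take other therapy while deferring, is not given, so the actual effect may be nil. The cycle 2 primary endpoint, the cycle 3 secondary endpoint and the 9-week disease control rate are not affected.

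**What to change.** 1. **Sections 3.1.3, 3.4, 4.1.2 and 3.5:** reconcile them so that one rule covers a patient who defers extension for other therapy. Which rule applies is the sponsor's decision.
2. **Sections 10.3.2 and 6.3.3.3:** end the ORR and best-response window at the earlier of the start of cycle 4 or the first non-protocol anti-cancer therapy.
3. **Sections 6.3.5 and 10.4.9:** state whether PFS follows patients through new therapy or censors at it, and show the other as a sensitivity analysis.
4. **Section 10.4.9:** report ADA and peak drug levels after cycle 3 separately for uninterrupted treatment, treatment holiday (with gap length) and intervening therapy. Do not attribute low titers after intervening therapy to tofacitinib alone. The objective in 1.1.3 can stay as a descriptive aim.
5. **Data collection:** record the start date of any intervening therapy. The annual call in the study calendar and the concomitant-treatment record in 4.1.2 do not explicitly require it.

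The cost is protocol wording and one data field. The downside is a possibly slightly lower ORR and smaller descriptive subgroups. Sample size and the primary decision rule are unchanged.
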